4.3 Clinical follow-up

(1) V1 screening period (-14 ~ 0 days)

If the patient has undergone relevant examinations before signing the informed consent form and within 14 days before surgery, these data can be collected as data for this clinical trial, and the patient does not need to undergo relevant examinations again. The following process should be completed:

- ◆ Sign the informed consent form;
- ◆ General information: date of birth, gender, height, weight;
- ◆ Vital signs: including blood pressure, heart rate/pulse, body temperature;
- ◆ Medical history: including hypertension, diabetes, coronary heart disease, stroke, allergies, surgical history, etc.;
- ◆ Inclusion criteria assessment;
- ◆ Laboratory tests;
- ◆ Standard electrocardiogram;
- ◆ AFEQT atrial fibrillation patient quality of life score sheet;
- ◆ Cardiac ultrasound;
- ◆ Medication status;
- ◆ Adverse events & serious adverse events;

(2) V2 Surgery (Day 0)

The following information should be collected/completed on the day of surgery:

- ◆ Medication status
- ◆ Adverse events & serious adverse events

(3) V3 Postoperatively (1-7 days, before discharge)

The following information needs to be collected/completed:

- ◆ Vital signs
- ◆ Laboratory tests
- ◆ Standard electrocardiogram
- ◆ AFEQT quality of life score for patients with atrial fibrillation
- ◆ Cardiac ultrasound

- ◆ Medication status
- ◆ Adverse events & serious adverse events

Post-discharge patient management recommendations:

Class I or Class III antiarrhythmic drugs can be used to maintain sinus rhythm within the 3-month window period after ablation or antiarrhythmic drugs.

Anticoagulants: Oral anticoagulation should be continued for at least 2 months after catheter ablation. After 2 months, anticoagulation can be selected based on the patient's CHA2DS2-VASc-60 score (see Appendix 14.3), rather than the effect of rhythm control (I, C). Male patients with a CHA2DS2-VASc-60 score of 1 or female patients with a CHA2DS2-VASc-60 score of 2 should consider discontinuing OAC 3 months after ablation, provided that there is no recurrence of atrial fibrillation under strict monitoring. Male patients with a CHA2DS2-VASc-60 score of 2 or female patients with a CHA2DS2-VASc-60 score of 3 without a history of stroke/TIA or systemic embolism should consider discontinuing OAC 3 months after ablation, provided that there is no recurrence of atrial fibrillation under strict monitoring. Male patients with CHA2DS2-VASc-60 score ≥ 3 or female patients with ≥ 4 , or patients with a history of stroke/TIA or systemic embolism, should consider long-term use of OAC after catheter ablation, regardless of whether it is successful or not.

Postoperative anticoagulation therapy monitoring plan

1. NOAC should be the first choice for NOAC/OAC treatment. NOAC has good efficacy and safety, and routine monitoring of coagulation function is not required during use. For patients who have received anticoagulation therapy with NOAC, liver and kidney function should be reviewed regularly and anticoagulation therapy should be adjusted in time.

2. Warfarin

After starting warfarin, INR should be tested once a day. After INR stabilizes, INR should be tested at least once a month to keep INR stable at 2.0~3.0 and TTR $\geq 70\%$.

(4) V4 1 month after surgery

During the follow-up visit $1m \pm 7d$ after surgery, the following information should be collected/completed:

- ◆ Vital signs
- ◆ Laboratory tests
- ◆ Standard electrocardiogram
- ◆ AFEQT quality of life score for patients with atrial fibrillation
- ◆ Cardiac ultrasound

- ◆ Medication status
- ◆ Adverse events & serious adverse events

(5) V6 3 months after surgery

The following information should be collected/completed during the $3m \pm 7d$ follow-up after surgery:

- ◆ Vital signs
- ◆ Laboratory tests
- ◆ Standard electrocardiogram
- ◆ AFEQT quality of life score for patients with atrial fibrillation
- ◆ Cardiac ultrasound
- ◆ Medication status
- ◆ Adverse events & serious adverse events

(6) V7 6 months after surgery

The following information should be collected/completed at the $6m \pm 15d$ follow-up after surgery:

- ◆ Vital signs
- ◆ Standard electrocardiogram
- ◆ Holter
- ◆ AFEQT quality of life score for patients with atrial fibrillation
- ◆ Cardiac ultrasound
- ◆ Medication status
- ◆ Adverse events & serious adverse events

(7) V8 12 months post-surgery

The following information should be collected/completed at the $12m \pm 15d$ follow-up after surgery:

- ◆ Vital signs
- ◆ Laboratory tests
- ◆ Standard electrocardiogram
- ◆ Holter
- ◆ AFEQT quality of life score for patients with atrial fibrillation
- ◆ Cardiac ultrasound

- ◆ Medication status
- ◆ Adverse events & serious adverse events

Note: Medication status: Record the medication status during the study period (from signing the informed consent to the end of follow-up). Routine solution preparation (normal saline, glucose solution), intraoperative anesthetics, and intraoperative anticoagulants do not need to be recorded. Drugs used for corrective treatment of adverse events also need to be recorded.

Adverse events: Record clinically significant adverse events of the subjects from signing the informed consent to the end of follow-up. Events in which the health status of the subjects does not deteriorate seriously due to planned hospitalization for existing diseases or follow-up required by the protocol are not recorded as serious adverse events.

5. End point

5.1. Primary endpoint:

Change in quality of life at 12 months as measured by the Atrial Fibrillation Quality of Life Survey (AFEQT). Improvement in quality of life from baseline to 12 months after pulsed field ablation procedure or AAD as measured by the Atrial Fibrillation Quality of Life Survey (AFEQT), with values ranging from 20 - 140 (higher scores mean worse outcomes).

5.2 Secondary endpoint:

- (1) The rate of atrial fibrillation-free recurrence during clinical follow-up within 12 months after surgery, that is, the success rate of pulsed field therapy for AF (including atrial tachycardia (AT) lasting more than 30 seconds, atrial flutter (AFL), and AF endpoint events);
- (2) Complications and adverse events during the pulsed field ablation surgery and during the postoperative follow-up, including readmission, cardiovascular events, cardiovascular death, all-cause death, and also including serious adverse events related to the surgery.
- (3) Rehospitalization due to heart failure or recurrence of atrial fibrillation 3 months after surgery;
- (4) The incidence of AT/AF/AFL events 3 months later.;
- (5) Improvement of cardiac function 6 and 12 months after surgery, including echocardiogram E/e', proBNP, etc.

6. Methods and timing for evaluating, recording and analyzing safety parameters

- (1) Record the occurrence of death, stroke or transient ischemic attack of the subjects during the study;

(2) Surgical operation-related parameters (operation time, left atrial operation time, number of ablation discharges, X-ray exposure time and X-ray radiation, etc.) and intraoperative complications: Observe and record the occurrence of surgery-related adverse events from the beginning to the end of the surgery. All adverse events should be tracked and followed up until they return to normal or baseline, or are sufficient to explain the abnormality. If the subject's participation in this trial ends, it should be tracked until the last follow-up;

(3) Clinically significant vital signs and related examinations:

Vital signs: Vital signs should be checked during the screening period, 1, 2, 3, 6 and 12 months of outpatient follow-up, and observed and recorded;

Laboratory examination: blood routine, blood biochemistry, coagulation function, electrolytes, coagulation function, NT-proBNP, D-dimer, myocardial enzyme spectrum and high-sensitivity cardiac troponin I are performed during the follow-up period. When clinically significant abnormal laboratory test results are found, they should be re-examined and followed up until they return to normal or have no clinical significance or baseline status; relevant laboratory tests need to be completed before the patient is discharged;

Standard electrocardiogram: 12-lead surface electrocardiogram is performed during the screening period, 1, 3, 6 and 12 months of follow-up;

Holter is used for follow-up at 3, 6 and 12 months after surgery.

Echocardiogram: The investigator may choose to perform transthoracic echocardiogram or/and transesophageal echocardiogram according to the patient's condition;

AFEQT Atrial Fibrillation Patient Quality of Life Scale: The patient's quality of life is scored during the screening period and 1, 3, 6 and 12 months after surgery;

(4) The occurrence of other adverse events and serious adverse events: Observe and record them throughout the trial. Serious adverse events should be tracked until the problem is resolved or the investigator determines that it has become "chronic" or "stable" or "sufficient to explain this abnormality". Reports of these adverse events should be recorded.

7. Safety evaluation

Safety refers to the absence of pulmonary vein stenosis, cardiac tamponade, phrenic nerve injury, esophageal injury, and femoral artery and vein injury, thrombosis/air embolism, myocardial infarction, stroke, TIA, asymptomatic cerebral infarction, coronary artery spasm, vagal reflex with severe bradycardia and other surgical complications during the perioperative period.

8. Time of participation in the study (each participation time and total time)

The time of participation in the study is the time when patients with persistent atrial fibrillation and HFpEF are planned to receive drug treatment or pulsed field ablation surgery, that is, the time of enrollment. The follow-up time is 1 month, 3 months, 6 months, and 12 months after enrollment. The total time is 12 months after the start of treatment. .

9. Data management and statistical analysis plan, data confidentiality plan

(1) The research data are managed and stored in the cardiology laboratory by full-time scientific research personnel.

(2) Data statistics and analysis

1. Statistical processing: SPSS22.0 statistical software was used for statistical analysis.
2. Normally distributed quantitative data, such as troponin, liver and kidney function, blood lipids, height, weight, EF, e/e', proBNP, etc.
3. Non-normally distributed quantitative data, such as age, are described as median ± interquartile range.
4. A t-test is planned for the results of molecular experimental data;
5. The composition ratio is used for statistical description of qualitative data, and the chi-square test is used for statistical inference. Cardiac function (NYHA classification) is tested using the K-W rank sum test;
6. $P < 0.05$ is considered significant.

10. Confidentiality Plan

The results of this project may be published in medical journals, but we will keep the patient's information confidential in accordance with the law. Unless required by relevant laws, the patient's personal information will not be disclosed. If necessary, government management departments and hospital ethics committees and their relevant personnel may review the patient's information in accordance with regulations.

11、Risk/Benefit Assessment

11.1 Personal Benefits: This study provides reasonable treatment strategies for patients' diseases according to the guidelines for the treatment of atrial fibrillation, which may help patients improve the symptoms and prognosis of atrial fibrillation.

Social Benefits: This study may delay the progression of atrial fibrillation, delay the related complications caused by atrial fibrillation, and may improve the quality of life. We hope that the

information obtained from your participation in this study will benefit you or patients with the same condition as you in the future.

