	
Life Survey (AFEQT), with values ranging from 20 - 140 (higher scores mean worse outcomes).
 
Secondary End Points
 
(1) The rate of atrial fibrillation-free recurrence during clinical follow-up within 12 months after surgery, that is, the success rate of pulsed field therapy for AF (including atrial tachycardia (AT) lasting more than 30 seconds, atrial flutter (AFL), and AF endpoint events);
 
(2) Complications and adverse events during the pulsed field ablation surgery and during the postoperative follow-up, including readmission, cardiovascular events, cardiovascular death, all-cause death, and also including serious adverse events related to the surgery.
 
(3) Rehospitalization due to heart failure or recurrence of atrial fibrillation 3 months after surgery;
 
(4) The incidence of AT/AF/AFL events 3 months later.;
 
(5) Improvement of cardiac function 6 and 12 months after surgery, including echocardiogram E/e', proBNP, etc.

Statistical analysis
	
OPC was analyzed based on previous clinical research data and used for comparison and evaluation of the main evaluation indicators. According to the current literature on the treatment of drug-refractory atrial fibrillation, the main evaluation indicator comparison target value was 80%.
 
1. Completion status and demographic analysis
 
Summarize the number of enrollments and completions of each center, and list the list of dropouts. Make a detailed list of the size of different data sets in each group, the distribution of cases in each center, the comparison of the total dropout rate, and the reasons for non-completion. Describe, analyze and evaluate the patient's demographic characteristics (age, gender, etc.), relevant medical history, treatment history, etc.
 
2. Safety evaluation
 
List the number and frequency of all adverse events, as well as the incidence of adverse events and serious adverse events. Make a cross-tabulation description of the changes in laboratory indicators before and after. The exact probability

	method was used to compare the two groups of adverse events.
--	--

Flow chart

Name	Screening period		Treatment period		Follow-up period			
	V1	V2	V3	V4	V5	V6	V7	
Visit point								
Visit time	-14d ~ 0d	0 d (Operation)	1-7 d (Before discharge)	1m ± 7d	3m ± 7d	6m ± 7d	12m ± 7d	
Informed consent	X							
General information	X							
Vital signs	X		X	X	X	X	X	
Medical history	X							
Inclusion criteria	X							

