Laboratory examination	X		X	X	X		X	
Standard electrocardiogram	X		X	X	X	X	X	
Holter					X	X	X	
AFEQT scale	X			X	X	X	X	
Echocardiogram	X		X	X		X	X	
Medication status	X	X	X	X	X	X	X	
Adverse events	X	X	X	X	X	X	X	

Note: m=month; d=day; h=hour.

(1) **V1 Screening period:** If the patient has undergone relevant examinations before signing the informed consent form and within 14 days before surgery, these data can be collected as data for this clinical trial. Patients do not need to undergo relevant examinations, such as laboratory tests, electrocardiograms, etc.

(2) **General information:** date of birth, gender, height, weight.

(3) **Vital signs:** body temperature, blood pressure, heart rate/pulse.

(4) **Medical history:** including hypertension, diabetes, coronary heart disease, stroke, allergies, surgical history, etc.

5) Pregnancy test: urine/blood pregnancy test (only for premenopausal women, only before surgery).

(6) Laboratory examination (V6 only measures NT-proBNP, and all other visits involving laboratory examinations (such as V1, V3 and V4) must complete all the following examination items):

Routine blood test: red blood cells (RBC), white blood cells (WBC), hemoglobin (Hgb), platelets (PLT); Blood biochemistry: alanine aminotransferase/alanine aminotransferase (ALT), aspartate aminotransferase/aspartate aminotransferase (AST), total bilirubin (TBIL), direct bilirubin (DBIL), blood urea nitrogen/urea (BUN/CREA), creatinine (Cr), uric acid (UA); ESR; Electrolytes: potassium ion (K); Coagulation function: prothrombin time (PT), activated partial thromboplastin time (APTT), fibrinogen (FIB); C β -reactive protein; D-dimer; NT-proBNP; myocardial enzyme spectrum and high-sensitive cardiac troponin T: lactate dehydrogenase (LDH), creatine kinase isoenzyme (CK-MB), and high-sensitive cardiac troponin I (hs-cTnI);

(7) Long-term Holter: Use a single-lead 7-day long-term Holter for monitoring.

(8) Medication status: Record the medication used during the study period (from the signing of the informed consent to the end of the follow-up). Routine fluid preparation (normal saline, glucose solution), intraoperative anesthetics, and intraoperative anticoagulants do not need to be recorded. Medication used for corrective treatment of adverse events also needs to be recorded.

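### The day-0 and first-week safety visits are tied to surgery and discharge with no stated drug-group equivalent, so early ascertainment may differ between the groups whose adverse events are tested

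*Protocol*

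**What the plan says.** **Visits V2 and V3.** In Protocol section 4.3, V2 is the operation day: "The following information should be collected/completed on the day of surgery", with medication status and adverse events as its only content. The next visit is "V3 Postoperatively (1-7 days, before discharge"; it lists vital signs, laboratory tests, ECG, AFEQT, cardiac ultrasound, medication and adverse events. The flow chart has the same anchor, "1-7 d (Before discharge". The flow-chart note on laboratory tests makes the V3 panel a complete one: "all other visits involving laboratory examinations (such as V1, V3 and V4) must complete all the following examination items". That panel includes troponin, CK-MB, D-dimer and C-reactive protein.

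**Both groups.** Section 8 defines entry as the point at which patients "are planned to receive drug treatment or pulsed field ablation surgery, that is, the time of enrollment", and continues: "The follow-up time is 1 month, 3 months, 6 months, and 12 months after enrollment". Section 2.2(2) names the same four times for comparing cardiac function, treatment effect and recurrence between the groups. Section 4.1 gives the drug group a Day 0, the start of the Class I or III drug, but uses it only to begin the 90-day blanking period. No visit or assessment is attached to it.

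**Safety recording and analysis.** Section 6 requires clinically significant laboratory abnormalities to be re-examined and followed. The only first-week test it names is tied to discharge: "relevant laboratory tests need to be completed before the patient is discharged". Adverse events are recorded from consent to the end of follow-up if clinically significant (notes to the flow chart and to section 4.3). The Summary, under safety evaluation, says that an exact probability "method was used to compare the two groups of adverse events".

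**The concern.** A patient who starts an antiarrhythmic drug need not have an operation date or a postoperative discharge. A site following the text therefore has no instruction to see or test that patient before the month-1 visit, while an ablated patient is examined within the first week by laboratory panel, ECG and ultrasound.

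A laboratory rise, a small effusion or an ECG change without symptoms is found only if a test is done. If such findings are judged clinically significant, they enter the adverse-event count for one group and have less chance of entering it for the other. The reverse also applies: an early problem after starting the drug that resolves before month 1 may never be elicited. Titration and repeated cardioversion are allowed in that interval (section 4.1), so it is not an empty one. Both effects push the comparison towards ablation looking less safe, and first-week information not collected in the drug group cannot be recovered later.

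**Working it through.** **1. Scheduled contacts after screening, from the flow chart.** The drug column applies if V2 and V3 have no counterpart.

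| Item | Ablation | Drug |
|---|---|---|
| Adverse-event contacts | 6 (V2-V7) | 4 (V4-V7) |
| Contacts with a laboratory visit | 4 (V3, V4, V5, V7) | 3 |
| ECG | 5 (V3-V7) | 4 |
| Ultrasound | 4 (V3, V4, V6, V7) | 3 |

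V2 carries no test, so every test row differs by exactly one visit, V3. Section 4.3 also lists ultrasound at 3 months, which the flow chart does not; that would make the last row 5 against 4 and leave the difference at one.

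**2. Drug group's first scheduled contact.** The visit is at 1 month ± 7 days. Taking a month as 30 days, this is day 23 to day 37.

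**3. Number per group.** Section 3.1 gives 63 evaluable per group (difference 10, SD 19.8, alpha 0.05, power 0.80). The noncentral t distribution gives power 0.8031 at n = 63, matching the stated 0.80306. With 20% dropout, 63 / (1 − 0.20) = 78.75, so 79 per group and 2 × 79 = 158. The plan's figures reproduce. They are used here only as the n for the adverse-event table.

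**4. Illustration of unequal detection.** The protocol gives no adverse-event rate and no rate of findings at V3, so both are assumptions:

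- p₀ = proportion of patients with a recorded event in the absence of V3 tests, the same in both groups: 10% or 20%.
- q = proportion of ablated patients in whom V3 tests yield a recordable finding, independently of p₀, that would have been equally common but unseen in the drug group: 0% to 20%.
- Recorded rate in the ablation group: p₁ = 1 − (1 − p₀)(1 − q). For example, p₀ = 0.20 and q = 0.10 give 1 − 0.80 × 0.90 = 0.28.

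The probability of a false signal is the sum, over all pairs of counts (i, j) with i > j and two-sided Fisher P < 0.05, of Bin(i; 79, p₁) × Bin(j; 79, p₀). Here i is the ablation count and j the drug count.

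| q | p₀ = 20%: p₁ | Ablation worse | Either direction | p₀ = 10%: p₁ | Ablation worse | Either direction |
|---|---|---|---|---|---|---|
| 0% | 20.0% | 1.6% | 3.2% | 10.0% | 1.4% | 2.8% |
| 2% | 21.6% | 2.9% | 3.8% | 11.8% | 3.4% | 3.9% |
| 5% | 24.0% | 6.3% | 6.6% | 14.5% | 9.3% | 9.5% |
| 10% | 28.0% | 16.8% | 16.9% | 19.0% | 28.7% | 28.7% |
| 20% | 36.0% | 54.5% | 54.5% | 28.0% | 78.8% | 78.8% |

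With 63 evaluable per group, the ablation-worse probabilities at q = 5%, 10% and 20% are 5%, 13% and 45% (p₀ = 20%) and 7%, 22% and 67% (p₀ = 10%).

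**The case against.** A reader might infer that V2 and V3 exist for the ablation group alone. The protocol does not say so:

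- The flow chart and section 4.3 form one schedule, not split by group, and the later visits, which section 8 applies to both groups, are also timed from surgery.
- Section 8 omits V2 and V3 for ablated patients too, and the flow chart separates a treatment period from the follow-up period. Its silence is therefore weak evidence about the drug group.
- Section 4.1 calls the drug group's cardioversion surgery, and the recommendations under V3 cover patients on antiarrhythmic drugs as well as ablated ones.

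All of this stands, and the point is accordingly one of a missing definition. It does not settle the matter the other way. Cardioversion is optional, and a drug starter still has no stated date on which V2 or V3 falls.

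A reader might also infer that a third of the ablation group's safety contacts (2 of 6) have no drug-group match in detection. That overcounts, because V2 has no tests and adverse events are recorded continuously in everyone, if clinically significant. What remains is findings seen only on a V3 test and transient early events that nobody asked about.

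Finally, a reader might conclude that the P value is shown to be invalid. It is not. At 2% extra detection, total rejection stays below 5% at both assumed rates. The model also counts every extra finding as an artefact, whereas some first-week events after ablation are real procedural harm. For that reason V3 findings should not simply be dropped from the main comparison: doing so could favour ablation.

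**Conclusion.** The point holds as a gap in definition with a plausible bias of unknown size. V2 and V3 are anchored to surgery and discharge, the drug group's Day 0 has no assessment attached, and the two groups' adverse events are to be compared by an exact test. Followed literally, early scheduled ascertainment is unequal, chiefly by the one V3 set of tests. If V2 and V3 were meant for both groups, sites cannot tell when to do them in the drug group. The text needs correcting on either reading.

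The direction, ablation looking worse, follows from the schedule if it is read literally. The magnitude does not: it rests wholly on the assumed event rates and the assumed V3-only detection. The lower end of the range (about 3% against about 1.5%) is of little consequence and the upper end is serious. Because only clinically significant findings count, the larger values are upper illustrations. The comparison affected is a safety one; the AFEQT primary endpoint is not touched by this point.

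**What to change.** 1. In section 4.3 and the flow chart, state what V2 and V3 mean for the drug group: anchor them to its Day 0 (start of the antiarrhythmic drug), with at least an adverse-event enquiry on days 1-7. A telephone call is enough, and no test is added.
2. Add a case-report-form field for how each event was detected (symptom or scheduled test) and at which visit.
3. In the Summary's safety evaluation, keep all events in the main two-group comparison. Add a supplementary comparison limited to serious or symptomatic events from each group's Day 0, plus test-detected findings at the shared visits (1, 3, 6 and 12 months). Show findings seen only on V3 tests separately for the ablation group.

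The cost is protocol wording, one form field, one short call per drug-group patient (79 calls at the planned size) and one extra table. The call does not reveal silent abnormalities in the drug group; the supplementary comparison is what addresses those. Reading the two comparisons together shows how far any difference depends on the V3 tests, without hiding procedural harm.

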Pulsed field ablation (PFA) is an emerging ablative energy. The basis for the damage effect of ablation is the voltage difference between the inside and outside of the membrane formed by the high-voltage electric field. This is electric field-dependent, does not generate heat locally, and has strong penetration ability. Under the action of high-voltage electric fields, the damage threshold of different tissues is different. The damage is selective to a certain extent, and it is safer for fragile adjacent tissues such as blood vessels, esophagus, and nerves^{9,10}. Currently, other energy forms used for ablation are not selective for this tissue type. In the global key study, the incidence of unsafe events for the product submitted this time was 0.7%, and no complications such as left atrial-esophageal fistula, pulmonary vein stenosis, myocardial infarction, phrenic nerve palsy, and

coronary spasm occurred. The extremely low incidence of unsafe events demonstrates the excellent safety of the product. Compared with existing technologies, the efficiency of PFA energy may also be improved. PFA delivery is completed in a few milliseconds, which may reduce isolation time and the entire operation time. By reducing the total operation time, the anesthesia time and the time the patient and doctor are exposed to radiation are reduced, which greatly improves the efficiency of the operation^{11,12}. The PulseSelect™ pulsed field ablation system is a ring electrode with a central support. Compared with a point-shaped radiofrequency catheter, it isolates the pulmonary veins by ablating a whole circle of 9 electrodes at the same time, further improving the efficiency of the operation. Due to the uniqueness and safety of its energy, it can significantly reduce postoperative complications and hospitalization time, shorten the patient's recovery period, and reduce the need for secondary treatment, thereby effectively reducing the patient's medical costs and economic burden¹³. The results of the Pulsed AF study also showed that at 6 and 12 months after surgery, the overall quality of life of patients (AFEQT and EQ-5D) increased by 5 points and 0.03 points respectively compared with the baseline level, and the results were statistically significant¹⁴. It can be seen that PFA reduces the overall medical resource investment by reducing the re-ablation rate and cardiovascular events.

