a) The CAPLA study compared the effects of PVI and PVI+PWI ablation strategies on quality of life. The average EF values of the two groups were 51.9 (12.1) vs. 52.6 (12.1), and the proportion of congestive heart failure was 71 (43.3%) vs. 70 (41.7%).

b) Long-term follow-up results showed that the AFEQT scores of PVI and PVI+PWI after catheter ablation were 88.9 (14.8) vs. 88.9 (14.8).

4. KiCS-Af study

a) The KiCS-AF study examined the effects of catheter ablation and drug therapy on heart failure with reduced ejection fraction and preserved ejection fraction, including patients with paroxysmal and persistent atrial fibrillation, with 83.4% of patients having LVEF >35%.

b) The baseline AFEQT in the catheter ablation and drug therapy groups was 71.3 (61.8–82.4) vs. 76.3 (63.0–87.0). The study classified the improvement in AFEQT scores into grades and performed a count analysis. According to the clinical significance of AFEQT improvement >5 points, the change gradient of 5 points, 10 points and 15 points was graded and the difference in the rates between the two groups was compared. There was no mean result.

5. RAFT-AF study

a) The RAFT-AF study evaluated the effects of catheter ablation and medication in patients with atrial fibrillation and heart failure. The proportion of patients with ejection fraction > 45% was 41% .

b) The AFEQT evaluation score was the difference between the baseline and follow-up nodes. The results of rate control versus catheter ablation rhythm control were 16.1 ± 1.6 versus 23.4 ± 1.5 .

Based on this sample size, only 3 cases in each group were required.

$$\delta = \mu_1 - \mu_2$$

Hypotheses: H0: $\delta = 0$ vs. H1: $\delta \neq 0$

Target Power	Actual Power	N1	N2	N	μ_1	μ_2	δ	σ_1	σ_2	Alpha
0.8	0.98614	3	3	6	16.1	23.4	-7.3	1.6	1.5	0.05

6. RCT STALL HFpEF

a) This is the first RCT on HFpEF, but the sample size is only 31 patients.

b) According to the AFEQT score results at six months, the results of the catheter ablation group and the drug therapy group were 75.2 ± 19.9 and 57.3 ± 23.5 , respectively. The sample size was calculated to be 25 cases in each group.

Numeric Results for an Unequal-Variance T-Test

$$\delta = \mu_1 - \mu_2$$

Hypotheses: H0: $\delta = 0$ vs. H1: $\delta \neq 0$

Target Power	Actual Power	N1	N2	N	μ_1	μ_2	δ	σ_1	σ_2	Alpha
0.8	0.81226	25	25	50	75.2	57.3	17.9	19.9	23.5	0.05

In view of the heterogeneity of the above study population and results, it is recommended that:

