1、 The AFEQT value of the endpoint of the pulse catheter ablation group be selected from the

CABANA heart failure cohort at 12 months, which is 80.6 (19.8). Referring to the KiCS-AF cohort study, which divided the AFEQT improvement value into three levels of 5, 10 and 15, we set the AFEQT value of the drug treatment group to 75.6/70.6/65.6.

2、 Set the AFEQT of the drug group to 75.6, $\alpha=0.05$, $\beta=0.2$, and 248 patients are required in each group.

Numeric Results for an Unequal-Variance T-Test

$$\delta = \mu_1 - \mu_2$$

Hypotheses: $H_0: \delta = 0$ vs. $H_1: \delta \neq 0$

Target Power	Actual Power	N1	N2	N	μ_1	μ_2	δ	σ_1	σ_2	Alpha
0.8	0.80138	248	248	496	80.6	75.6	5	19.8	19.8	0.05

3、 Set the AFEQT of the drug group to 70.6, $\alpha=0.05$, $\beta=0.2$, and 63 cases are needed in each group. Considering a dropout rate of 20%, 79 cases are needed in each group.

Numeric Results for an Unequal-Variance T-Test

$$\delta = \mu_1 - \mu_2$$

Hypotheses: $H_0: \delta = 0$ vs. $H_1: \delta \neq 0$

Target Power	Actual Power	N1	N2	N	μ_1	μ_2	δ	σ_1	σ_2	Alpha
0.8	0.80306	63	63	126	80.6	70.6	10	19.8	19.8	0.05

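### The primary endpoint is defined with higher AFEQT scores as worse, but the adopted sample-size scenario treats higher scores as better

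*Protocol*

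**What the plan says.** The endpoint is defined twice in the same terms. Section 5.1 describes AFEQT "with values ranging from 20 - 140 (higher scores mean worse outcomes", and the End point row of the Summary repeats this: "Life Survey (AFEQT), with values ranging from 20 - 140 (higher scores mean worse outcomes". Both places describe the endpoint as an improvement from baseline to 12 months.

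Section 3.1 reviews several studies and then fixes the planning values. The ablation mean is taken from the "CABANA heart failure cohort at 12 months, which is 80.6 (19.8" being the SD. The drug mean is derived from a cohort study "which divided the AFEQT improvement value into three levels of 5, 10 and 15", and on that basis "we set the AFEQT value of the drug treatment group to 75.6/70.6/65.6". The last scenario worked through is "Set the AFEQT of the drug group to 70.6", which gives 63 per group and 79 after 20% dropout. Earlier in section 3.1 the same cohort study is described in these words: "According to the clinical significance of AFEQT improvement >5 points, the change gradient of 5 points, 10 points and 15 points was graded".

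Section 1 (Background) reports for an earlier pulsed field ablation study that "the overall quality of life of patients (AFEQT and EQ-5D) increased by 5 points and 0.03 points respectively compared with the baseline level", and presents this as a benefit.

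**The concern.** The endpoint definition says a high score is bad. The sizing scenario gives the high score to ablation and obtains the drug value by taking an improvement step away from it, which makes sense only if a high score is good. Both cannot hold for the same score.

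A two-sided p-value shows that the arms differ, and the scoring direction shows which arm did better. If scores are collected with higher as better and then interpreted under the section 5.1 label, a real benefit of ablation could be reported as harm, or a harm as benefit. The study is multicentre, so sites could also score or read the questionnaire in different directions.

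**Working it through.** **1. Reproduce the plan's figure.** Inputs from section 3.1: means 80.6 and 70.6, SD 19.8 in each group, two-sided alpha 0.05, target power 0.80, dropout 20%.

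- Standard error of the difference at n = 63 per group: √(2 × 19.8² / 63) = √(784.08 / 63) = 3.528.
- Noncentrality: 10 / 3.528 = 2.83, with 2 × 62 = 124 degrees of freedom.
- Power from the noncentral t distribution: 0.8031 (the plan prints 0.80306). At n = 62 it is 0.7967, so 63 is the smallest n.
- Dropout: 63 / (1 − 0.20) = 78.75, rounded up to 79. Total 2 × 79 = 158, the sample size in the Summary.

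The arithmetic is right, and the total of 158 confirms that the 70.6 scenario was adopted.

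**2. Read the direction from how the drug means were built.** Compare them with what the section 5.1 label would require for a drug arm that is worse by the same step.

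| Step | Drug mean in section 3.1 | Drug mean if higher is worse |
|---|---|---|
| 5 | 80.6 − 5 = 75.6 | 80.6 + 5 = 85.6 |
| 10 | 80.6 − 10 = 70.6 | 80.6 + 10 = 90.6 |
| 15 | 80.6 − 15 = 65.6 | 80.6 + 15 = 95.6 |

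All three values are subtractions, so this is not a slip in one figure.

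**3. Look for support elsewhere.** The Background treats a 5-point rise in AFEQT as a gain, which agrees with section 3.1. The 12-month scores quoted from CABANA (86.4 vs 80.9) and its heart failure cohort (80.6 vs 75.0), and the six-month scores from the HFpEF randomised trial (75.2 vs 57.3), all have ablation higher. They fit the same direction but do not prove it, because section 3.1 does not say which arm did better. The RAFT-AF changes are left aside because the order of subtraction is not given. No section states a conversion, a reversed score, or that two scorings are in use.

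**4. Size of the contradiction, if the section 3.1 values are on the 20–140 scale.** The range is 140 − 20 = 120.

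- Ablation is worse than drugs by 80.6 − 70.6 = 10 points: 10 / 120 = 8.3% of the range.
- The two readings of the adopted drug mean differ by 90.6 − 70.6 = 20 points: 20 / 120 = 16.7% of the range.

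**5. Does N depend on it?** Sign alone: a difference of −10 with SD 19.8 again gives power 0.8031 at 63 per group, so 79 and 158 stand.

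Scale is a separate matter, because section 3.1 gives no score range. As an illustration only, assume its values are on a 0–100 scale with higher better, which the protocol does not say. A reversed linear conversion to 20–140 gives:

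- ablation: 140 − 1.2 × 80.6 = 43.3; drug: 140 − 1.2 × 70.6 = 55.3;
- difference 12, SD 1.2 × 19.8 = 23.76. The ratio is unchanged, so n is still 63.

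If only the SD were converted and the difference stayed at 10, power at 63 per group would be 0.65. The requirement would then be 90 per group, and 90 / 0.8 = 112.5, rounded up to 113, after dropout.

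**The case against.** The strongest reply is that little depends on this. The hypothesis in section 3.1 is non-directional, the sample size is the same for either sign, and section 9 has no AFEQT rule that uses the sign. Section 3.1 never states a direction in words; it has to be inferred from the subtraction and from the word improvement, which in the cited cohort graded changes in score and is reused here as a gap between arms. Reporting a benefit as harm would require scores collected one way and read the other, and the protocol shows no scoring instruction from which to tell whether that will happen. The percentages of the 120-point range also mean something only if the section 3.1 values are on that scale.

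Much of this is fair. N is safe against a change of sign, the percentages are conditional on a shared scale, and misreporting is a risk rather than a demonstrated outcome. But the inference about direction is secure: no reading under which higher is worse explains why all three drug values were obtained by subtracting an improvement from the ablation value. Nor can this be left to an analysis plan, since the protocol itself fixes range and direction in two places and contradicts them in its own sizing.

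**Conclusion.** The concern holds. The protocol gives the score of its only primary endpoint one direction where it is defined and the opposite direction where the study is sized, and does not reconcile them. On the section 5.1 label, and assuming a shared scale, the planning scenario has ablation 10 points worse than drug therapy. The total of 158 is unaffected by the sign, and no loss of power is claimed. The check in section 3.1 concerns 12-month scores rather than change from baseline and is used here only to show that the sign does not move N. The document does not establish which statement is wrong, although the Background sides with section 3.1. Because the contradiction can reverse the primary conclusion, it must be corrected before AFEQT results are analysed.

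**What to change.** Take the range and direction from the instrument's scoring rule and state them identically in the Summary, section 3.1 and section 5.1. There are two ways to do this:

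- correct the 20–140, higher-is-worse label so that it matches the score used for planning; or
- keep that label and convert the planning means, the difference and the SD in section 3.1 to that scale together, since converting only some of them would change the sample size.

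In either case, state which sign of the change from baseline to 12 months is favourable, and check that the AFEQT score sheet and the case report form used at all centres follow the same rule.

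The cost is wording in three places, the conversion if the second route is taken, and a check of the scoring rule. No extra patients or visits are needed.
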